## MODIFICATION HISTORY

Unique Identifier for this Version	Date of the Document Version	Author	Significant Changes from Previous Authorized Version
Version 1.0	02 Dec 2023	[REDACTED]	Initial version
Version 2.0	23 Apr 2024	[REDACTED]	
Updated following TLFs per Organon team review.
 

• Updated Table 14.1.1.1 Participant Disposition, clarified the calculation of percentages.

• Removed Tables 14.3.4.1 Markedly abnormal lab test.

• Added Tables 14.3.4.1 through 14.3.4.3 Actual and change from baseline in lab tests by visit in hematology, chemistry, and urinalysis.

• Added Listing 14.3.5.1 Markedly Abnormal liver function tests.

• Corrected/updated Section 16 Appendix A.

• Changed the definition of treatment compliance in Table 14.1.7.1.

• Just keep two visits of baseline and last measurement and remove other visits in

---

Document:

[REDACTED]

Author:

[REDACTED]

Version Number:

2.0

Version Date:

23APR2024

Template No.: CS\_TP\_BS016 Revision 6

Reference: CS\_WI\_BS005

Effective Date: 02Dec2019

Copyright © 2009, 2010, 2012, 2016, 2018, 2019 [REDACTED] All rights reserved. The contents of this document are confidential and proprietary to [REDACTED] and its subsidiaries. Unauthorized use, disclosure or reproduction is strictly prohibited.

## LIST OF ABBREVIATIONS

Abbreviation	Term
AE	Adverse Event
APS	Allocated Participants Set
ATC	Anatomical Therapeutic Chemical
BMI	Body Mass Index
CTMS	Clinical Trial Management System
DBP	Diastolic Blood Pressure
eCOA	electronic Clinical Outcome Assessment
eCRF	electronic Case Report Form
ECI	Event of Clinical Interest
ENR	All Participants Enrolled
EOS	End Of Study
EOT	End Of Treatment
MedDRA	Medical Dictionary for Regulatory Activities
MES	Multiple Enrollment Set
PT	Preferred Term
SAE	Serious Adverse Event
SAF	Safety Analysis Set
SAP	Statistical Analysis Plan
SBP	Systolic Blood Pressure
SI	International System of Units
SOC	System Organ Class

Document:

[REDACTED]

Author:

[REDACTED]

Version Number:

2.0

Version Date:

23APR2024

Template No.: CS\_TP\_BS016 Revision 6

Reference: CS\_WI\_BS005

Effective Date: 02Dec2019

Copyright © 2009, 2010, 2012, 2016, 2018, 2019 [REDACTED]. All rights reserved. The contents of this document are confidential and proprietary to [REDACTED] and its subsidiaries. Unauthorized use, disclosure or reproduction is strictly prohibited.

Abbreviation	Term
TEAE	Treatment-Emergent Adverse Event
WBC	White Blood Cells
WHODrug	World Health Organization Drug Dictionary

---

Document:

Author:

Version Number:

2.0

Version Date:

23APR2024

Template No.: CS\_TP\_BS016 Revision 6

Reference: CS\_WI\_BS005

Effective Date: 02Dec2019

Copyright © 2009, 2010, 2012, 2016, 2018, 2019 [REDACTED]. All rights reserved. The contents of this document are confidential and proprietary to [REDACTED] and its subsidiaries. Unauthorized use, disclosure or reproduction is strictly prohibited.

## 1. INTRODUCTION

Due to early termination of the study, the sponsor decided to report study results in a synoptic report focusing on safety data. This document describes the rules and conventions to be used in the presentation and analysis of safety data for protocol OG-8175A-023. It describes the data to be summarized and analyzed, including specifics of the statistical methods and analyses to be performed.

This statistical analysis plan (SAP) is based on protocol Amendment 2, dated 30AUG2022.

### 1.1. IMPORTANT DEFINITIONS

**Treatment cycle:** A treatment cycle is defined by the period between 2 start dates of a blister, as recorded in the participant's e-Diary.

**Evaluable cycle (at risk):** cycles with duration 22 to 35 days (inclusive) with affirmed heterosexual vaginal intercourse and lack of additional contraception use. In cases of a confirmed pregnancy, cycles that start after the estimated date of conception (as determined by the investigator based on gestational age from an ultrasound) will not be considered "at risk".

**On-treatment period for pregnancies:** the period from the first date of intake of study treatment up to and including 7 days after the last date of study treatment intake.

- **Pre-treatment pregnancies:** pregnancies with an estimated date of conception before the first date of study treatment intake. Also, all pregnancies in participants in which all dispensed trial treatment is returned unused (per investigator's record) will be considered pre-treatment.
- **On-treatment pregnancies:** On-treatment pregnancies are pregnancies with an estimated date of conception between the first date of intake of study treatment up to and including 7 days after the last date of study treatment. In the absence of an ultrasound, the earliest positive serum/urine test date will be utilized to classify pregnancy category. In this case, an on-treatment pregnancy is defined as a positive serum/urine pregnancy test date that is more than 7 days after the first pill and not more than 14 days after the last pill.
- **Post-treatment pregnancies:** Post-treatment pregnancies are pregnancies with an estimated date of conception after the on-treatment period as defined above. In the absence of ultrasound results, post-treatment pregnancy is defined as a positive serum/urine pregnancy test date that is more than 14 days after the last pill.

Final determination for pre/during/post treatment will be made by the clinical team.

Document: [REDACTED]

Author: [REDACTED]

Version Number:

2.0

Version Date:

23APR2024

Template No.: CS\_TP\_BS016 Revision 6

Reference: CS\_WI\_BS005

Effective Date: 02Dec2019

Copyright © 2009, 2010, 2012, 2016, 2018, 2019 [REDACTED]. All rights reserved. The contents of this document are confidential and proprietary to [REDACTED] and its subsidiaries. Unauthorized use, disclosure or reproduction is strictly prohibited.

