8.4.1 Time Period and Frequency for Collecting AE and SAE Information

All AEs and SAEs will be collected from the signing of the ICF until EOS/ET (Section [1.3](#)).

From the time of signing ICF through EOS/ET(V7), which is 14 to 19 days after last intake of study drug, all AEs, SAEs, and other reportable safety events must be reported by the Investigator. For the analysis of AEs and SAEs, a distinction will be made between:

- **Pre-Treatment AEs:** Events which occur after the ICF (or assent form, if applicable) is signed and before the first intake of study drug.
- **Treatment-emergent AEs:** Events which occur in temporal association with intake of study drug, until 14 days after the last intake of active study drug.

Additionally, any SAE brought to the attention of an Investigator at any time outside the period specified in the previous paragraph must be reported immediately (within 24 hours of learning about the event) to the Sponsor if the event is considered related to study drug.

Investigators are not obligated to actively seek AEs or SAEs or other reportable safety events in former study participants. However, if the Investigator learns of any SAE, including a death, at any time after a participant has been discharged from the study, and he/she considers the event to be reasonably related to the study drug or study participation, the Investigator must promptly notify the Sponsor.

All initial and follow-up AEs, SAEs, and other reportable safety events will be recorded and reported to the Sponsor or designee within the time frames as indicated in [Table 8](#).

The method of recording, evaluating, and assessing causality of AE and SAE and the procedures for completing and transmitting SAE reports are provided in [Appendix 4](#).

Table 8 Reporting Time Periods and Time Frames for Adverse Events and Other Reportable Safety Events

Type of Event	Reporting Time Period: Signing of ICF to First Intake of Study Drug (Day 1)	Reporting Time Period: First Intake of Study Drug (Day 1) through End of Study (V7)	Time Frame to Report Event and Follow-up Information to Sponsor:
Nonserious Adverse Event (NSAE)	Report if: 
• Due to protocol-specified procedure, or• Causes exclusion	Report all	Per eCRF completion guidelines
Serious Adverse Event (SAE)	Report if: 
• Due to protocol-specified procedure, or• Causes exclusion	Report all	Within 24 hours of learning of event

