9.4.2 Efficacy Analyses

9.4.2.1 Contraceptive Efficacy Endpoints

9.4.2.1.1 Definitions

An on-treatment pregnancy is defined as a pregnancy with an estimated date of conception from the day of first intake of study drug up to and including 7 days after the last intake of active study drug.

A pre-treatment pregnancy is defined as a pregnancy with an estimated date of conception after signing informed consent, but before the first intake of study drug. Also, all pregnancies in

[figure not shown]
[figure not shown]
[figure not shown]
[figure not shown]
[figure not shown]
participants in which all dispensed study drug is returned unused (per Investigator's record) will be considered pre-treatment pregnancies.

A post-treatment pregnancy is defined as a pregnancy with an estimated date of conception more than 7 days after the last intake of active study drug.

See Section 8.2.1.2.1 for confirming reported pregnancies and determining conception date.

A treatment cycle is defined by the period between 2 start dates of a blister, as recorded in the participant's e-Diary. The last treatment cycle ends by the last recorded day of tablet intake.

An at-risk cycle for pregnancy is a treatment cycle in which the participant has used no contraceptives of any type other than the study drug *and* in which the participant has affirmed heterosexual vaginal intercourse.

[figure not shown]14 days.
- Prolonged bleeding (FDA definition): At least one bleeding/spotting episode starting within an RP, with a length of >7 days.

The RPA will be conducted on the following endpoints for the FAS evaluable:

- Number of bleeding days, spotting days, and bleeding-spotting days
- Proportion of participants with the following:
 - Amenorrhea;
 - Infrequent, frequent, or normal frequency bleeding-spotting; and
 - Prolonged bleeding-spotting.
- Mean duration of bleeding-spotting episodes defined as abnormal uterine bleeding that occur between periods.

Data Handling Conventions

The same data handling conventions as for the cycle analysis will be used concerning the interpolation rule for missing bleeding information and the imputation of “no bleeding” for the first 7 days of RP1.

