9.4.3 Safety Analysis

The APaT population will be used for all safety analyses.

Safety and tolerability will be assessed by clinical review of all relevant parameters including AEs, laboratory values, vital signs, and body weight.

For the analysis of safety data, the following conventions will be used:

- Baseline will be defined as the last measurement before the first study drug intake.
- The on-treatment period will be defined as the period from the day of first tablet intake up to and including the day of last active study drug intake, extended by 14 days. However, any delayed events or diagnoses judged by the Investigator to be related to study drug will also be considered to have occurred on-treatment and will be included in the safety analysis.
- Last measurement is the last value obtained during the on-treatment period.

The proportion of participants with prespecified events listed as ECIs described in Section 8.4.5 during the on-treatment period will be provided along with corresponding 95% Clopper-Pearson CIs. All ECIs will be summarized, even if the incidence is zero.

In addition, the broad AE categories consisting of the percentage of participants with any AE, a drug-related AE, a serious AE, an AE, which is both drug-related and serious, and who discontinued study drug due to an AE will be summarized with corresponding 95% Clopper-Pearson CIs (Table 10). On-treatment AEs are those occurring from first intake of study drug to 14 days after intake of the last active tablet of study drug. AEs occurring during the designated pre-treatment (between V1 and first intake of study drug) and post-treatment (>14 days after last tablet intake of study drug) periods will be provided.

Table 10 Analysis Strategy for Safety Parameters

Safety Endpoint ^a	Within Group 95% CI ^b	Descriptive Statistics
Any AE	X	X
Any Serious AE	X	X
Any Drug-Related AE	X	X
Any Serious and Drug-Related AE	X	X
Discontinuation due to AE	X	X
Specific AEs, SOCs, ECIs, and PDLCs (incidence ≥ 4 participants)		X
Specific AEs, SOCs, ECIs, and PDLCs (incidence < 4 participants)		X
Change from Baseline Results (laboratory tests, vital signs)		X

Abbreviations: AE=adverse event; CI=confidence interval; ECI=event of clinical interest; PDLC=Predefined Limit of Change; SOC=System Organ Class; X=results will be provided.

a. AE references refer to both clinical and laboratory AEs.

b. 95% CIs will be calculated using the Clopper-Pearson method.

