## 6.5. WINDOWING CONVENTIONS

The on-treatment period for safety assessments will be defined as the period from the day of the first tablet intake up to and including the day of the last tablet intake, extended by 14 days after last tablet.

Windows shown in Table B will be used in the analysis of vital signs and laboratory parameters for analyses performed per visit. Values outside these visit windows, or outside the defined on-treatment period for post-baseline assessments, will be excluded from the analysis of that particular visit. However, no values will be excluded from listings or for the determination of markedly abnormal laboratory (unless outside the defined in-treatment period). If more than one observation is available within a specific visit window, the latest value will be used for analysis.

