### 15.1. ADVERSE EVENTS

AEs will be coded using MedDRA coding dictionary, Version 26.1 or higher.

Treatment-emergent adverse events (TEAEs) are defined as AEs that started on or after the day of first dose of study treatment (or worsened in severity) and prior to the last date of study treatment + 14 days (inclusive). See Appendix A for handling of partial dates for AEs. In the case where it is not possible to define an AE as treatment emergent or not due to a partial start date, the AE will be classified by the worst case; i.e. treatment emergent. Pre-treatment AEs/SAEs starting before the on-treatment period, including those starting on the day of first dose of study treatment yet prior to the study treatment intake, will be excluded from the TEAE analyses. Pre- and post-treatment AEs will be identified in listings.

---

Document: [REDACTED]

Author: [REDACTED]

Version Number:

2.0

Version Date:

23APR2024

Template No.: CS\_TP\_BS016 Revision 6

Reference: CS\_WI\_BS005

Effective Date: 02Dec2019

Copyright © 2009, 2010, 2012, 2016, 2018, 2019 [REDACTED]. All rights reserved. The contents of this document are confidential and proprietary to [REDACTED] and its subsidiaries. Unauthorized use, disclosure or reproduction is strictly prohibited.

An overview table of number (%) of participants within each of the categories described in the sub-section below will be provided as specified in the templates. The broad AE categories consisting of the percentage of participants with any TEAE, a drug-related TEAE, a serious TEAE, a TEAE that is both drug-related and serious, and a TEAE leading to discontinuation of study treatment will be summarized. Similar Table by BMI group ( $<30 \text{ kg/m}^2$ ,  $\geq 30 \text{ kg/m}^2$ ) will be provided. Listings will include all AEs (including participants who enrolled more than once).

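### SAP 1.1 runs the on-treatment window for pregnancies from the last tablet of any kind, where the protocol runs it from the last active tablet, and SAP 3.2 does not declare the change

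*SAP*

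**What the plan says.** **Pregnancies.** Protocol 9.4.2.1.1 defines an on-treatment pregnancy by a conception date "from the day of first intake of study drug up to and including 7 days after the last intake of active study drug". Protocol 8.2.1 uses the same limit. Protocol 8.2.1.2 and Appendix 5 use it again to define the potentially exposed pregnancies that must be followed to their outcome. SAP 1.1 instead ends the window "up to and including 7 days after the last date of study treatment intake". Where there is no ultrasound, it accepts a positive test dated "not more than 14 days after the last pill". SAP 7.1 has a similar fallback that uses the first and last dose dates.

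**Adverse events and other safety data.** Protocol 9.4.3 ends the on-treatment period "up to and including the day of last active study drug intake, extended by 14 days", and protocol 8.4.1 counts treatment-emergent events "until 14 days after the last intake of active study drug". SAP 6.5 runs the period "up to and including the day of the last tablet intake, extended by 14 days after last tablet", and SAP 15.1 and Appendix A follow it.

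**Declared changes.** SAP 3.2 lists the restriction to safety analyses, the analysis sets, and a correction of the laboratory and vital-sign limit from 28 to 14 days. It does not mention the move from last active tablet to last tablet.

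**The concern.** The SAP states that it is based on Amendment 2, whose current text says active. The word was chosen on purpose: the Amendment 1 change table (Protocol Table 13) records adding it to the definitions of on-treatment and post-treatment pregnancy. A colleague who reads SAP 3.2 as the full list of departures would assume that the pregnancy classes in the report follow the protocol.

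At stake is the class printed beside a pregnancy in the listing. A conception shortly after a finished blister could be listed as on-treatment although the protocol calls it post-treatment and does not count it among the potentially exposed pregnancies to be followed up.

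**Working it through.** **Can the SAP's anchor be a placebo tablet?** Yes. Protocol 6.0 includes placebo in its definition of study treatment. SAP 3.1 has one tablet of study treatment taken daily through 28-day cycles of 24 active and 4 placebo days.

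**Reproduce the plan's own duration.** 13 × (24 + 4) = 364 days, and 364 / 7 = 52 weeks, as stated.

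**Completer with all tablets on schedule.**
- Last active tablet: 12 × 28 + 24 = Day 360.
- Last tablet: 13 × 28 = Day 364. The gap is 4 days.
- Pregnancy window, protocol: 360 + 7 = Day 367.
- Pregnancy window, SAP: 364 + 7 = Day 371.

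**By the last tablet taken, on schedule** (window end in days after the last active tablet):

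| Last tablet number | Gap (days) | Protocol | SAP |
|---|---|---|---|
| 1–24 | 0 | 7 | 7 |
| 25 | 1 | 7 | 8 |
| 26 | 2 | 7 | 9 |
| 27 | 3 | 7 | 10 |
| 28 | 4 | 7 | 11 |

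After a complete blister, the conceptions that change class are therefore those 8 to 11 days after the last active tablet. If the last 1, 2 or 3 active tablets are missed and all four placebo tablets are taken, the gap is 28 − (24 − m), that is 5, 6 or 7 days for m = 1, 2, 3. Four days is the on-schedule maximum, not an absolute one.

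**Adverse events.** The same arithmetic gives 360 + 14 = Day 374 under the active-tablet wording and 364 + 14 = Day 378 under the SAP. Here, however, the protocol has two anchors. Protocol 9.4.3 ends the on-treatment period 14 days after the last active tablet but starts the post-treatment AE period more than 14 days after the last tablet. For a completer, Days 375 to 378 then belong to neither period. The footnote to Protocol Table 11 also counts from the last tablet.

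**What re-anchoring SAP 6.5 would do.** Visit 7 is due 14 days after last intake, with a window of +5 days: Day 378 to Day 383 for a completer, or 18 to 23 days after the last active tablet. A limit at Day 374 would put every such visit outside the on-treatment period. SAP 6.5 excludes post-baseline values outside that period from the per-visit analysis, and Visit 7 holds the only scheduled post-baseline hematology and biochemistry. The SAP's limit of Day 378 admits a Visit 7 held on its target day.

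**The case against.** The best case against the point has four parts.

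1. **The SAP governs.** Protocol 9.4 says that the SAP prevails where the two differ, and the SAP states its anchor openly in several places. This stands: the operative rule is not in doubt, and an attentive reader can find it. It does not explain why a departure from four consistent protocol passages is missing from the section that lists departures.
2. **Little depends on it.** Efficacy is not analysed, so no Pearl Index moves. Pregnancies are only listed (SAP 15.6), and SAP 1.1 leaves the final classification to the clinical team. This stands and limits the weight of the point.
3. **Percentages exaggerate.** Going from 7 to 11 days is a 57% longer tail (4/7), but for a completer the whole window grows by 4/367, about 1.1%. This also stands, so the size is best given in days.
4. **The last active date may not be directly recorded.** Protocol 8.2.3.1 describes e-Diary entries for blister start and daily intake, not tablet number. This is a fair reason to ask for a written derivation rule. Protocol 8.2.3.2 already treats Days 1 to 24 as the active period, so the date should be derivable.

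A reader might also infer that the SAP's safety window is wrong in the same way and should return to the last active tablet. The documents do not support that. For AEs the protocol contradicts itself, the SAP's wording closes the unassigned days, and re-anchoring would push Visit 7 outside the window.

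**Conclusion.** The pregnancy definition in SAP 1.1 departs from the protocol without being declared. It lengthens the window by 1 to 4 days when the final tablet is a placebo tablet taken on schedule, by more if late active tablets were missed, and not at all for women who stop during the active phase. It can only move pregnancies from post-treatment to on-treatment. The documents give no count of affected pregnancies, and none can be derived from them.

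For AEs the finding is narrower: the last-tablet window is a workable answer to a protocol inconsistency, and the omission is that SAP 3.2 does not say so. That window can only add treatment-emergent events. For laboratory and vital-sign limits, the protocol's Table 11 footnote already used the last tablet, and the change from 28 to 14 days is declared.

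The day counts assume one tablet per day in blister order and, unless stated otherwise, no missed tablets.

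**What to change.** 1. **SAP 1.1 and 7.1:** count the 7-day pregnancy window from the last active tablet, and state that the last-pill and last-dose fallbacks for pregnancies without an ultrasound date use the same anchor.
2. **Derivation rule:** define the last active date as the last e-Diary day with recorded intake within Days 1 to 24 of the final blister, going back to the previous blister if there is none. State how missed or doubled tablets and missing diary days are handled.
3. **AEs:** leave SAP 6.5, Table B, 15.1 and Appendix A on the last tablet. Add to SAP 3.2 that the treatment-emergent window runs from the last tablet, and that this resolves the two anchors in protocol 9.4.3.
4. **AE listing:** flag events that start more than 14 days after the last active tablet but inside the SAP window.

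The cost is a few sentences in the SAP, one derived date with its rule, and one listing flag. No new data are needed.

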## 2. OBJECTIVES AND ENDPOINTS

Only safety objectives and endpoints will be analyzed as outlined in Table A.

**Table A Study Objectives and Endpoints**

Objectives	Endpoints
Primary	
To assess the safety and tolerability of the NOMAC-E2 COC	

• Proportion of participants who had an adverse event

• Abnormalities in clinical laboratory assessments, vital signs, and physical examination

• Proportion of participants who prematurely discontinued study treatment due to adverse events

Abbreviations: COC=combined oral contraceptive; NOMAC-E2=Nomegestrol Acetate + 17 $\beta$ -estradiol

